6.5. STATISTICAL TESTS

In general, unless stated otherwise, continuous variables will be summarized using descriptive statistics (number of patients, mean, standard deviation [SD], median, minimum and maximum values) and for categorical (nominal) variables, the number and percentage of patients will be used.

The default significant level will be 5%; CIs will be 95% and all tests will be two-sided, unless otherwise specified in the description of the analyses.

6.6. COMMON CALCULATIONS

- Change from baseline: Test Value at Visit X – Baseline Value
- Percentage change from baseline:

$$\frac{\text{Test Value at Visit X} - \text{Baseline Value}}{\text{Baseline Value}} * 100\%$$

6.7. ACTUAL TREATMENT

Once the study unblinds, the patient's actual treatment will be assigned based on the most frequent medication they have received throughout the study. Patients are only expected to receive either 3 mg of ensifentrine, or placebo. The external vendor, Cenduit, will provide the Material List document after confirmation of a DBL. This document will contain the kit numbers, which will be merged with the site data to obtain the treatment that was dispensed at each visit.

If a patient takes more than one medication and the ratio of actual treatments taking the placebo

and ensifentrine is the same, then the patient will be assigned ensifentrine.

6.8. SOFTWARE VERSION

All analyses will be conducted using SAS version 9.4 or higher.

6.9. STRATA CALCULATIONS

There are three separate stratification factors used: treatment duration (48 or 24 weeks), background maintenance therapy strata and smoking strata. For all factors planned and actual will be created.

For treatment duration strata:

- Planned – As recorded in the Cenduit report.
- Actual – The actual treatment duration in which the patient consented to in the Patient Consent form
-
- In case when the randomized treatment duration stratum does not match with the treatment duration the patient consented to, the patient will be assigned to the stratum they consented to.

For background maintenance therapy strata:

- Planned – As recorded in the Cenduit report.
- Actual - As recorded in the “Concomitant medications” eCRF page: Patients that take LAMA or LABA (or LAMA/ICS or LABA/ICS) medication with start date being before or on randomization date and end date is either ongoing/post-randomization are classified as being on background maintenance therapy strata. Patients that do not meet this criteria will be classified as “No”.

For smoking strata:

- Planned – As recorded in the Cenduit report.
- Actual – As recorded in the “COPD and Smoking History” eCRF page.

6.10. RUSSIAN LABORATORIES

At the start of the study, the laboratory data collected from Russian sites were to be collected from the central sources. However, from 23 March 2022, which is the date of the first collection

[REDACTED]

[REDACTED]

[REDACTED]

[REDACTED]

[REDACTED]

from local laboratory reported in Inform, the data have been coming from either central or local sources. These sources use different ranges for laboratory parameters.

The laboratory ranges will be entered by the sites directly into the eCRF if done by a local laboratory or if received by a data transfer from InVitro laboratories. All units will be converted to conventional or SI units for consistency of the original Q2 laboratory tests received prior to the implementation of using InVitro or the local laboratories to indicate low/normal/high categories. Any alert or flag variable in the received data that indicates its category will not be used.

7. STATISTICAL CONSIDERATIONS

7.1. ADJUSTMENTS FOR COVARIATES AND FACTORS TO BE INCLUDED IN ANALYSES

The following covariates and factors are used in the analyses. For details of their inclusion in the models, see the specific analysis section.

Fixed effects: treatment (ensifentrine, placebo), region (Asia, Europe, North America), visit (Day 1, Week 6, Week 12, Week 18, Week 24), visit*treatment, stable background maintenance of LABA or LAMA (or LAMA/ICS or LABA/ICS) therapy use (yes, no), cigarette smoking (current, former)

Random effect: patient

Covariate: baseline

In case when the analysis model does not converge, the factor that causes it will be removed from the model.

7.2. MULTICENTER STUDIES

This study will be conducted by multiple investigators at multiple centers internationally. Randomization to treatment arms is not stratified by country/ center.

When specified, statistical analysis will be adjusted for geographic region. Geographic region will be categorized as shown in Table 3.

[REDACTED]	[REDACTED]	[REDACTED]	[REDACTED]
[REDACTED]	[REDACTED]	[REDACTED]	[REDACTED]
[REDACTED]	[REDACTED]	[REDACTED]	[REDACTED]
[REDACTED]	[REDACTED]	[REDACTED]	[REDACTED]

Table 3: Geographic Regions

Geographic Region	Country
Asia	Republic of Korea
Europe	Bulgaria, Czech Republic, Germany, Greece, Hungary, Poland, Romania, Russian Federation, Slovakia, United Kingdom
North America	United States

7.3. MISSING DATA

Missing safety data will not be imputed.

All data collected during the scheduled visits for patients on-treatment and off-treatment, for patients with treatment withdrawal, as well as the end-of-study visits for patients withdrawing from the study will be used for analysis performed on the mITT and that the remaining missing values will be handled as described in Sections 16.1.2, 16.2.2 and 16.3.2 of the SAP.

7.4. MULTIPLE COMPARISONS/ MULTIPLICITY

To address multiplicity in the analysis of the endpoints, statistical testing of the primary endpoint and key secondary endpoints will be done in the hierarchical order (listed below). Initially the primary endpoint will be checked to see if comparison between active treatment and placebo is statistically significant. If yes, the first key secondary endpoint will be evaluated. If yes, the next key secondary endpoint will be evaluated. This process will continue until either all endpoints are evaluated, or if one of the endpoints' comparison is not significant.

Order of the endpoints that will be used for the hierarchical testing:

1. Change from baseline FEV₁ to FEV₁ AUC_{0-12h} at Week 12
2. Change from baseline FEV₁ to peak FEV₁ at Week 12
3. Change from baseline (i.e. mean over the last 7 days of run-in) to the mean weekly value at Week 24 in COPD symptoms, as measured by daily diary (E-RSTM:COPD)
4. Change from baseline in the SGRQ total score at Week 24
5. Change from baseline FEV₁ to morning trough FEV₁ at Week 12
6. Change from baseline FEV₁ to average FEV₁ AUC_{0-4h} at Week 12
7. Proportion of SGRQ responders at Week 24

7.5. EXAMINATION OF SUBGROUPS

Subgroup analyses will be conducted as stated in the efficacy analysis and disposition sections.

[REDACTED]	[REDACTED]	[REDACTED]	[REDACTED]
[REDACTED]	[REDACTED]	[REDACTED]	[REDACTED]
[REDACTED]	[REDACTED]	[REDACTED]	[REDACTED]
[REDACTED]	[REDACTED]	[REDACTED]	[REDACTED]

Primary aim for the subgroup analysis is to check whether there are differences in treatment effect between strata or subgroups, which will be tested through interaction. For each analysis by subgroup the results will be summarized as follows:

- Complete data with added fixed effect to the model: subgroup*treatment.
- Data split by subgroup using the main model.

The following subgroups will be assessed and described within the analysis Sections 16.1.4 and 16.2.4 of the SAP.

- Gender at birth:
 - Female
 - Male
- Age-class (years):
 - <65
 - ≥65
- Region
 - Asia
 - Europe
 - North America
- Actual Background medication strata
 - Yes
 - No
- Actual Smoking strata
 - Current
 - Former
- Actual ICS use
 - Yes
 - No
- Known chronic bronchitis
 - Yes
 - No
- FEV₁ reversibility at screening (≥12% and ≥200mL increase in FEV₁)
 - Yes
 - No
- COPD severity

[Redacted content]

- Mild (post-bronchodilator dose $FEV_1 \geq 80\%$ predicted)
- Moderate ($50\% \leq$ baseline $FEV_1 < 80\%$ predicted)
- Severe ($30\% \leq$ baseline $FEV_1 < 50\%$ predicted)
- Very severe (baseline $FEV_1 < 30\%$ predicted)

All the four categories of COPD severity will be included in the patient disposition presentations. However, when used in efficacy analysis, only the two subgroups with moderate and severe patients will be used in the analysis models.

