9.0 STATISTICAL CONSIDERATIONS

9.1 Statistical Hypotheses

The aim of this study is to show superiority of ensifentrine over placebo regarding selected efficacy measures. The null hypothesis to be tested for each endpoint will be that there is no difference between ensifentrine and placebo, against the alternative hypothesis that ensifentrine is better than placebo. All tests will be two-sided at a 5% significance level. Primary and key secondary endpoints used for claims will be tested in a sequential order to preserve the alpha level. Testing will stop once a not significant result is achieved. Test order will be FEV₁ AUC_{0-12h} at 12 weeks, peak FEV₁ at 12 weeks, weekly mean E-RS total symptom score at week 24, SGRQ total score at 24 weeks, morning trough FEV₁ at Week 12, FEV₁ AUC_{0-4h} at 12 weeks and proportion of SGRQ responders at Week 24.

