9.2 Sample Size Determination

Approximately 800 patients will be randomized. The standard deviation for the change in FEV₁ AUC_{0-12h} is estimated to be 250 mL. With a 2-sided test at a 5% significance level and 500 vs. 300 evaluable patients in the two groups, there will be an 90% power to detect a true difference of 59 mL between the treatments. If the withdrawal rate at 24 weeks exceeds 25% overall, additional patients may be randomized to the study to compensate for the loss of data.

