16.1.3. PRIMARY ANALYSIS OF PRIMARY EFFICACY VARIABLE

The primary objective of this study is to test the hypothesis that there is a difference between ensifentrine in comparison with placebo.

The change from baseline FEV₁ to average FEV₁ AUC_{0-12h} will be compared between ensifentrine and placebo using ANCOVA with fixed effects for treatment, region, background medication strata and smoking strata and baseline FEV₁ as covariate. Missing data will be imputed using imputation described in Section 16.1.2 of the SAP. The estimated treatment difference will be presented with 95% CI and associated p-value. Furthermore, SD will be presented for the treatment difference to check the sample size with 90% power. Summary statistics will be performed on the imputed values.

Model assumptions will be tested as per the following rules on the blinded data, before the DBL.

1. Residual vs Predicted plots will be created to check residuals are uncorrelated and normally distributed.
2. Normality of the data will be checked using Kolmogorov-Smirnov normality test.

If any of the checks specified above fail the test, then alternative approaches will be discussed, including different ways of transposing data. The SAP will be updated to reflect any changes prior to DBL.

Only spirometry measurements with best test review (BTR) grades “Acceptable” and “Borderline Acceptable” are used in the analysis and baseline calculations.

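### Read literally, the subgroup interaction test in SAP 7.5 omits the subgroup main effect for six factors, so it mixes prognosis with effect modification

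*SAP*

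**What the plan says.** SAP 7.5 states the purpose of the subgroup work: to "check whether there are differences in treatment effect between strata or subgroups, which will be tested through interaction". It lists two outputs for each subgroup. One is the main model fitted separately within each subgroup level. The other, which supplies the test, is "Complete data with added fixed effect to the model: subgroup*treatment".

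The main model is defined in SAP 16.1.3 as "ANCOVA with fixed effects for treatment, region, background medication strata and smoking strata and baseline FEV₁ as covariate". SAP 7.5 lists nine subgroup factors. Region, background medication and smoking already appear in that model. Gender, age class, ICS use, chronic bronchitis, FEV1 reversibility and COPD severity do not, and no section adds their main effects. SAP 16.2.4 carries the same subgroup analysis over to the key secondary endpoints. Protocol 9.4.1 lists subgroups but gives no model.

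**The concern.** An interaction test should ask whether the treatment difference varies between subgroups. If a factor enters only through its product with treatment, that term must also absorb any difference in outcome between subgroups that is common to both arms. A factor that merely predicts change in FEV1 can then give a small p-value labelled as interaction.

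At stake is the section's declared main aim. A spurious result could suggest that efficacy differs by sex, age, ICS use or severity when it does not. With the primary and up to six key secondary endpoints, as many as 7 × 6 = 42 tests use this wording.

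**Working it through.** **Inputs.** From Protocol 9.1 and 9.2: "All tests will be two-sided at a 5% significance level"; the SD of the primary endpoint "is estimated to be 250 mL"; "500 vs. 300 evaluable patients in the two groups". The prognostic effect *d* of a subgroup is an assumption (20, 40, 60 mL), as is subgroup prevalence *p* (50% and 20%). The 20% case matches the ceiling on ICS users in Protocol 4.1.

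**The plan's own figure.** The protocol says "there will be an 90% power to detect a true difference of 59 mL between the treatments". SE = 250 × √(1/500 + 1/300) = 18.26 mL; 59/18.26 = 3.23; power = Φ(3.23 − 1.96) = 0.898. This agrees with 90% and confirms the inputs. The point below does not depend on it.

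**Degrees of freedom, binary factor.** Treatment plus subgroup\*treatment fits four cell means. Removing the added term leaves two (one per arm), so the term has 4 − 2 = 2 df. Its null hypothesis is that the subgroups do not differ within either arm. With the subgroup main effect present, removing the interaction leaves three parameters, so the test has 4 − 3 = 1 df. Its null is then that the treatment difference is the same in both subgroups, which is the question SAP 7.5 asks. COPD severity is restricted to moderate and severe in the efficacy models, so all six factors are binary there.

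**Rejection rate with no true interaction.** The 2-df F statistic has noncentrality λ = 800 × p(1 − p) × d² / 250². The critical value of F(2, 796) at 5% is 3.007. For example, p = 0.5 and d = 40 give 800 × 0.25 × 1600 / 62500 = 5.12.

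| Prevalence | d (mL, assumed) | λ | Noncentral F | Simulation |
|---|---|---|---|---|
| 50% | 20 | 1.28 | 16% | 15% |
| 50% | 40 | 5.12 | 51% | 52% |
| 50% | 60 | 11.52 | 87% | 87% |
| 20% | 20 | 0.82 | 12% | 12% |
| 20% | 40 | 3.28 | 35% | 33% |
| 20% | 60 | 7.37 | 68% | 67% |

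The simulation used a common 59 mL treatment effect and 4,000 trials per scenario (2,000 for the 20% subgroup). A separate simulation at 25 and 50 mL gave 23% and 72% for a 50/50 subgroup. There, the test with the main effect included rejected in 4.8% of trials (50% prevalence) and 4.3% (20% prevalence) at every prognostic effect from 0 to 100 mL, which is nominal within simulation error. With no prognostic effect the 2-df test was also nominal, at about 5%.

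**Other coding.** If the term is entered as a single product column, the rates at 25 and 50 mL are 21% and 62% (50/50 subgroup), and the estimated interaction reproduces the prognostic effect: about 51 mL when the prognostic effect is 50 mL and the true interaction is zero.

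**Factors already in the model.** With the main effect present, as for region, background medication and smoking, a binary factor with a 100 mL prognostic effect gave 5.5% rejection on 1 df.

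**The case against.** The strongest reply is that the line is shorthand: it names the term that supplies the test and never says the main effect is left out. That is possible, and the output shells, which might settle it, are not available here. But SAP 7.1 and the MMRM in SAP 16.2.4 both list main effects separately from the interaction, and SAP 7.5 speaks of one added effect. Code that follows the line literally would run without complaint and give the wrong test.

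A second reply is that the millilitre effects are hypothetical. That stands: the documents give no prognostic effects, and 60 mL is as large as the 59 mL treatment difference used for sample size. Baseline FEV1 may absorb part of a severity effect. ICS is allowed only with a LAMA or LABA, so the background term may absorb part of an ICS effect. The percentages are illustrations, not forecasts.

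A reader might go further and infer that any prognostic subgroup will be reported as a treatment interaction. The documents do not support that. Three of the nine factors already have their main effects in the model. For the other six the error is a probability that depends on the size of the prognostic effect: at an assumed 20 mL most trials would show nothing. Nor can one infer that the efficacy conclusions are at risk. The subgroup tests lie outside the hierarchy in SAP 7.4, the split-by-subgroup estimates do not use this term, and with treatment and subgroup coded as class variables the within-subgroup differences from the interaction model are also correct. Only the interaction p-value is wrong; under single-column coding the interaction estimate is wrong too.

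**Conclusion.** The point holds for six factors: gender, age class, ICS use, chronic bronchitis, FEV1 reversibility and COPD severity. For these, the model as written does not test what SAP 7.5 says it will test, and its false-positive rate for interaction is above 5% whenever the factor is prognostic. The tabulated sizes rest on assumed prognostic effects, 500:300 patients, an SD of 250 mL and no baseline covariate.

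Region, background medication and smoking are sound on one condition. SAP 7.5 uses the actual background and smoking strata, SAP 6.9 derives planned and actual versions, and SAP 16.1.3 does not say which the ANCOVA uses. The two must match. The correction should be made, but primary and key secondary inference does not depend on it.

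**What to change.** Replace the model line in SAP 7.5 with wording to this effect: *main model on the full data, plus a fixed effect for subgroup (where its main effect is not already in the model, using the same version of the strata) and a fixed effect for subgroup by treatment; the interaction p-value comes from the latter, with (number of subgroup levels − 1) df.* Limiting the added main effect to factors not already in the model avoids duplicating region, background medication and smoking.

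State in SAP 16.1.3 whether planned or actual strata are used. The cost is one phrase in each section and one model term in the program. If shorthand was intended, nothing else changes.

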4.0 STUDY DESIGN

4.1 Overall Design

RPL554-CO-301 is a multicenter, randomized, double blind, parallel group, placebo controlled study to determine the efficacy and safety of ensifentrine 3 mg twice daily (BID) for 24 weeks with a subset of patients for 48 weeks, administered via nebulizer vs. placebo in patients 40 to 80 years of age with moderate to severe COPD (FEV₁ 30% – 70% of predicted, FEV₁/ forced vital capacity [FVC] ratio <0.7, with documented COPD symptoms).

Approximately 50% of patients recruited will be using stable background maintenance as *either* long-acting muscarinic antagonist (LAMA) *or* long-acting β 2 agonist (LABA) maintenance therapy and all patients will be provided with rescue albuterol/salbutamol for use as needed during the study. Up to 20% of patients are allowed to take inhaled corticosteroids during the study under certain provisions (see Sections 6.7.2 and 6.7.3). Washout of patients on stable background maintenance LAMA or LABA monotherapy for the sole purpose of study eligibility is not recommended.

Randomization will be stratified by three different factors: treatment duration (48 or 24 weeks), stable background maintenance LAMA or LABA therapy use (yes or no), and cigarette smoking (current or former). The 48 weeks strata will be randomized active to placebo 3:1, and the 24 weeks strata will be randomized active to placebo 1:1. Patients in the background maintenance LAMA or LABA therapy stratum must withhold Twice-Daily maintenance LAMA or LABA (or LAMA/ICS or LABA/ICS) for 24 hours and Once-Daily maintenance LAMA or LABA (or LAMA/ICS or LABA/ICS) for 48 hours prior to initiation of any spirometry. All patients must withhold short acting bronchodilator (SABA) rescue medication for at least 4 hours prior to initiation of any spirometry. All sites will use standardized spirometry and ECG equipment provided by a central vendor and all spirometry and ECGs will be over-read by the blinded central vendor.

Patients will be screened for eligibility before entering a 28-day run-in period to ensure a stable background maintenance LAMA or LABA bronchodilator medication regimen and to collect baseline information on symptoms and rescue medication use. Permitted rescue and background medications and the condition of their use during the study are described in Section 6.7.2. Prohibited medications and the prohibited time intervals prior to Screening are described in Section 6.7.3.

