8. Maintenance Therapy: Patients on no maintenance/background therapy or patients on stable maintenance as *either* LAMA *or* LABA therapy are eligible. Patients taking maintenance LAMA or LABA therapy must demonstrate regular use of maintenance LAMA or LABA therapy, in any form, for at least 2 months prior to Screening and agree to continue use of their current permitted LAMA or LABA medication for the duration of the study. Section 6.7.3 lists the medications that are prohibited during the study and the prohibited time intervals prior to Screening. Approximately 50% of patients will be enrolled using background maintenance LAMA or LABA bronchodilator therapy.

Other Requirements for Inclusion

9. Capable of withholding SABAs for 4 hours prior to initiation of any spirometry. Patients in the maintenance LAMA or LABA therapy stratum must be capable of withholding Twice-Daily maintenance LAMA or LABA for 24 hours and Once-Daily maintenance LAMA or LABA for 48 hours prior to initiation of any spirometry.
10. Capable of using the study nebulizer correctly and complying with all study restrictions and procedures.
11. Ability to perform acceptable spirometry in accordance with ATS/ERS guidelines (Miller 2005).

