6.7.2 Permitted Rescue and Background Medications

Permitted rescue and background medications are provided in Table 7.

Any vaccine that is recommended by the patient’s healthcare provider is permitted during the study (e.g. COVID, influenza, pneumonia), and should be recorded in the eCRF.

Table 7: Permitted Rescue and Background Medications

Medication	Condition
Albuterol/salbutamol	Used as rescue medication as needed during the study. Must be withheld for at least 4 hours prior to spirometry. ¹ Should be withheld for at least 4 hours prior to ECGs.
Either LAMA or LABA	Patients entering the study on a maintenance regimen of either LAMA or LABA therapy will be required to remain on that regimen at a stable dose for the duration of the study. Dual LAMA/LABA therapy is not allowed. Stable ICS use is allowed along with a LAMA or LABA maintenance regimen if it was initiated at least 4 weeks prior to Screening. ICS monotherapy is not allowed. Must withhold prior to spirometry: Twice-Daily maintenance LAMA or LABA (or LAMA/ICS or LABA/ICS) for 24 hours and Once-Daily maintenance LAMA or LABA (or LAMA/ICS or LABA/ICS) for 48 hours, including at Visit 1. ¹ The maintenance LAMA or LABA (or LAMA/ICS or LABA/ICS) therapy should resume once all spirometry for a given visit has been completed.
No maintenance or background therapy	Patients entering the study on no maintenance background therapy will not be allowed to initiate background maintenance therapy for COPD (ie, maintenance LAMA or LABA therapy, or ICS therapy) for the duration of the study.
Inhaled corticosteroids (ICS)	Stable use of ICS is permitted IF the patient has been taking the ICS at least 4 weeks prior to Screening (Visit 0) AND the patient is also taking maintenance LABA or LAMA. ICS should not be initiated or discontinued during the study. ICS monotherapy and high dose ICS (e.g. >1000 mcg of fluticasone propionate or equivalent) is not allowed.
¹ If the withholding periods are not met the visit should be rescheduled to be held within 3 days of the scheduled visit. Abbreviations: COPD=chronic obstructive pulmonary disease; LAMA= long-acting muscarinic antagonist; LABA= long-acting β 2 agonist	

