6.7.3 Prohibited Medications/Therapy

Prohibited medications and therapies are provided in Table 8.

Table 8: Prohibited Medications/Therapy

Medication	Time Interval
Oral, Systemic or Parenteral Steroid Therapies	3 months prior to Screening Visit and prohibited during the study. ¹
Antibiotics for lower respiratory tract infection	6 weeks prior to Screening Visit and prohibited during the study. ¹ Chronic use of antibiotics is not allowed 6 weeks prior to or during the study.
Inhaled Corticosteroids (ICS) (e.g. ICS monotherapy and patients in the no maintenance therapy stratum) High dose ICS (e.g. >1000 mcg of fluticasone propionate or equivalent)	4 weeks prior to Screening Visit and prohibited during the study.
Oral leukotriene inhibitors (i.e. montelukast, zafirlukast, zileuton)	48 hours prior to Screening Visit and prohibited during the study.
Theophylline and PDE4 inhibitor (e.g. roflumilast, apremilast, crisaborole)	48 hours prior to Screening Visit and prohibited during the study.
Terbutaline	1-day prior to Screening Visit and prohibited during the study.
Ipratropium (including combinations with albuterol/salbutamol)	6 hours prior to Screening Visit and prohibited during the study.
LAMA/LABA combination products	4 weeks prior to Screening Visit and prohibited during the study.
Nebulized LAMA or LABA or ICS For patients in the no maintenance therapy stratum: For patients in the LAMA or LABA stratum:	4 weeks prior to Screening Visit and prohibited during the study. 1-week prior to Screening Visit and prohibited during the study (e.g. patient should switch from nebulized to dry powder or metered dose therapy)
LAMA Excluded ONLY for patients in the no maintenance therapy stratum	4 weeks prior to Screening Visit and prohibited during the study. ²
LABA Excluded ONLY for patients in the no maintenance therapy stratum	4 weeks prior to Screening Visit and prohibited during the study. ²
Oral beta ₂ -agonists	1-week prior to Screening Visit and prohibited during the study.

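### The ICS-by-treatment interaction test in SAP 7.5 mixes ICS use with background LAMA/LABA use, so part of any background-by-treatment difference will appear in it

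*SAP*

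**What the plan says.** Protocol 6.7.2 (Table 7) allows stable ICS only if the patient has used it for at least four weeks before Screening "AND the patient is also taking maintenance LABA or LAMA". Protocol 6.7.3 (Table 8) prohibits ICS otherwise, giving as examples "ICS monotherapy and patients in the no maintenance therapy stratum". SAP 6.9 counts LAMA/ICS and LABA/ICS users as background-yes.

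On the mix, Protocol 4.1 says "Up to 20% of patients are allowed to take inhaled corticosteroids during the study" and inclusion criterion 8 in Protocol 5.1 says "Approximately 50% of patients will be enrolled using background maintenance LAMA or LABA bronchodilator therapy".

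Protocol 9.4.1 lists ICS use among the subgroups. SAP 7.5 carries it as "Actual ICS use", Yes or No, with no restriction to the background stratum. Each subgroup is analysed in two ways. One is "Complete data with added fixed effect to the model: subgroup*treatment"; the other reruns the main model separately in each subgroup. The main model (SAP 16.1.3) has treatment, region, background strata and smoking strata as fixed effects and baseline FEV1 as covariate. It has no background-by-treatment term. Background strata is a separate subgroup in the same list. No planned analysis looks at ICS within the background-yes stratum or fits the two interactions together.

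**The concern.** By protocol rule, ICS-yes is a subset of background-yes, and the whole background-no stratum falls in ICS-no. The two ICS groups therefore differ in bronchodilator background by design as well as in ICS. A background main effect shifts both treatment arms by the same amount, so it cannot absorb a difference in treatment effect between background strata. In the ICS-yes split the background factor is constant, apart from protocol deviations.

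SAP 7.5 gives the purpose of the subgroup analyses as checking, by interaction test, whether the treatment effect differs. For ICS the planned test cannot say whether a difference it finds, or fails to find, belongs to ICS or to LAMA/LABA. The amendment that admitted ICS users rested on the expectation that stable ICS use would not affect the endpoints, so readers are likely to look to this result for reassurance.

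**Working it through.** **The plan's own figure.** Protocol 9.2: SD 250 mL, 500 vs 300 patients, difference 59 mL, two-sided 5%. SE = 250 x sqrt(1/500 + 1/300) = 18.26 mL; 59/18.26 = 3.23; power = Φ(3.23 - 1.96) = 89.8%. This agrees with the stated 90%, so the same SD and 5:3 allocation are used below.

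**Composition at N = 800, 50% background, 20% ICS.**
- ICS-yes: 160 patients, all background-yes.
- ICS-no: 640 patients, of whom 400 are background-no (400/640 = 62.5%) and 240 background-yes (37.5%).

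In general the background-no share of ICS-no is (1 - b)/(1 - i), with b the background share and i the ICS share:

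| b | i = 5% | i = 10% | i = 15% | i = 20% |
|---|---|---|---|---|
| 45% | 57.9% | 61.1% | 64.7% | 68.8% |
| 50% | 52.6% | 55.6% | 58.8% | 62.5% |
| 55% | 47.4% | 50.0% | 52.9% | 56.2% |
| 60% | 42.1% | 44.4% | 47.1% | 50.0% |

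**Leakage.** Let d be the treatment effect in background-no minus that in background-yes, and let ICS have no effect of its own. The ICS-no effect then exceeds the ICS-yes effect by (background-no share) x d, which is 0.625 x d at the 20% cap.

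**Standard error of the ICS interaction.** With 5:3 allocation, ICS-yes splits 100/60 and ICS-no 400/240. SE = 250 x sqrt(1/100 + 1/60 + 1/400 + 1/240) = 45.6 mL.

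**False-signal rate.** With z = 0.625d/45.6, the rate is 1 - Φ(1.96 - z) + Φ(-1.96 - z). The values of d are assumptions.

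| d (mL) | Spurious ICS difference (mL) | Nominal rejection at 5% |
|---|---|---|
| 25 | 15.6 | 6.4% |
| 50 | 31.3 | 10.5% |
| 75 | 46.9 | 17.7% |
| 100 | 62.5 | 27.8% |

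**Simulation.** 4,000 trials per scenario, N = 800, no ICS effect, background as a main effect, ICS and ICS-by-treatment in the model. The spurious difference and rejection rate were 62.8 mL and 27.6% at d = 100 mL, and 31.2 mL and 10.8% at d = 50 mL. At d = 0 rejection was 5.6%. If SAP 7.5 is read literally, with the interaction but no ICS main effect, leakage at d = 100 mL is smaller but remains: 28.0 mL, 15.5% rejection.

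**After the change.** With background-by-treatment added, the mean ICS estimate at d = 100 mL was within 1 mL of zero and rejection was 5.2%. Within background-yes, 160 ICS (100/60) against 240 non-ICS (150/90) gives SE = 250 x sqrt(1/100 + 1/60 + 1/150 + 1/90) = 52.7 mL.

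**The case against.** The strongest reply is that SAP 7.5 does not claim to isolate a causal ICS effect. A marginal Yes/No comparison is the usual consistency check, and the ICS-yes split does estimate the treatment effect in ICS users. That stands, and it is why the split should be kept. It does not rescue the interaction test as evidence about ICS.

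The overlap is also partly visible. Background strata has its own interaction test, so any d that could leak is itself estimated, and the baseline tables (SAP section 10) break background use into LAMA, LAMA/ICS, LABA and LABA/ICS. This helps a careful reader but does not separate the two effects.

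The size of d is open. A reader might take 100 mL from Protocol 2.2, which reports peak FEV1 effects above 200 mL without maintenance bronchodilators and above 100 mL on tiotropium at the two highest doses. The documents do not support that as an estimate. It subtracts two lower bounds from two separate four-week studies, and on peak FEV1 rather than the primary endpoint. For average FEV1 over 12 hours, Protocol 2.2 gives 87 mL on tiotropium at 3 mg but no matching figure without background therapy. This trial also withholds LAMA or LABA for 24 or 48 hours before spirometry, which may shrink d for lung function. E-RS and SGRQ lack that protection to the same degree, but no d can be drawn from the documents for either.

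**Conclusion.** The point holds as a matter of structure: the planned ICS interaction test carries part of any background-by-treatment difference. At 50% background and 20% ICS that part is 0.625 x d; at 5% ICS it is about 0.53 x d. A reader might infer that a background difference will be reported in full as an ICS effect. It will not: the leakage is partial and disappears if d = 0. Nor is it certain that most ICS-no patients are without background therapy. That follows from the planned mix, but the share falls to half or less at, for example, 55% background with 10% ICS or fewer.

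The 16-63 mL and 6-28% figures rest on the assumed d of 25-100 mL, SD 250 mL, 5:3 allocation and the 20% ICS cap. Subgroup analyses lie outside the testing hierarchy in SAP 7.4, so the primary and key secondary results are not affected. This is an inexpensive improvement to how one subgroup result is tested and read.

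**What to change.** In SAP 7.5, keep the protocol-listed ICS Yes/No split as a description. Base the ICS-by-treatment interaction test on background-yes patients, comparing LAMA or LABA with ICS against LAMA or LABA without ICS. In effect the same contrast comes from the full population if background-by-treatment is fitted alongside ICS and ICS-by-treatment. Apply this wherever the ICS subgroup is analysed, including the key secondary endpoints (SAP 16.2.4).

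The cost is a few lines of SAP text and one further model. No new data are needed, since ICS and background use are already recorded and tabulated together at baseline. The ICS contrast becomes less precise: its SE rises from about 45.6 to 52.7 mL at SD 250 mL and 20% ICS, about 15% wider (52.7/45.6 = 1.16 on these rounded figures).
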